8.3.2 Serious Adverse Events

A **serious adverse event** (SAE) is any adverse experience occurring at any dose that results in any of the following outcomes:

- Results in **death**.
- Is a **life-threatening** adverse experience. The term life-threatening in the definition of serious refers to an adverse event in which the subject was at risk of death at the time of the event. It does not refer to an adverse event which hypothetically might have caused death if it were more severe.
- Requires **inpatient hospitalization or prolongation of existing hospitalization**. Any adverse event leading to hospitalization or prolongation of hospitalization will be considered as Serious, UNLESS at least one of the following expectations is met:
 - The admission results in a hospital stay of less than 24 hours OR
 - The admission is pre-planned (e.g., elective or scheduled surgery arranged prior to the start of the study) OR

- The admission is not associated with an adverse event (e.g., social hospitalization for purposes of respite care).

However it should be noted that invasive treatment during any hospitalization may fulfill the criteria of “medically important” and as such may be reportable as a serious adverse event dependant on clinical judgment. In addition where local regulatory authorities specifically require a more stringent definition, the local regulation takes precedent.

- Results in **persistent or significant disability/incapacity**. The definition of disability is a substantial disruption of a person’s ability to conduct normal life’s functions.
- Is a **congenital anomaly/birth defect**.
- Is an **important medical event**. Important medical events that may not result death, be life-threatening, or require hospitalization may be considered a serious adverse experience when, based upon appropriate medical judgment, they may jeopardize the subject and may require medical or surgical intervention to prevent one of the outcomes listed in this definition. Examples of such medical events include allergic bronchospasm requiring intensive treatment in an emergency room or at home, blood disease or disorders, or convulsions that do not result in inpatient hospitalization, or the development of drug dependency or drug abuse. The development of a new cancer is always considered an important medical event.

For the purpose of this study the following events would not be considered adverse events and would not be recorded in the database:

- Abnormal laboratory findings considered associated to the original disease

8.3.3 Adverse Event Evaluation

The investigator or designee is responsible for ensuring that all adverse events (both serious and non-serious) observed by the clinical team or reported by the subject which occur after the subject has signed the informed consent are fully recorded in the subject’s medical records. Source documentation must be available to support all adverse events.

A laboratory test abnormality considered clinically relevant (e.g., causing the subject to withdraw from the study, requiring treatment or causing apparent clinical manifestations, result in a delay or dose modification of study treatment, or judged relevant by the investigator), should be reported as an adverse event.

The investigator or sub-investigator (treating physician if applicable) will provide the following for all adverse events (both serious and non-serious):

- Event term (as per CTCAE)
- Description of the event
- Date of onset and resolution
- **Expectedness of the toxicity**
- **Grade of toxicity**
- **Attribution of relatedness to the investigational therapy/agent- (this must be assigned by an investigator, sub-investigator, or treating physician)**
- Action taken as a result of the event, including but not limited to; no changes, dose interrupted, reduced, discontinued, etc. or action taken with regard to the event, i.e. no action, received conmed or other intervention, etc.
- Outcome of event

Descriptions and **grading scales** found in the NCI Common Terminology Criteria for Adverse Events (CTCAE) version **4.0** will be utilized for agent AE reporting.

An expected adverse event is an event previously known or anticipated to result from participation in the research study or any underlying disease, disorder, or condition of the subject. The event is usually listed in the Investigator Brochure, consent form or research protocol.

An unexpected adverse event is an adverse event not previously known or anticipated to result from the research study or any underlying disease, disorder, or condition of the subject.

Attribution is the relationship between an adverse event or serious adverse event and the study drug. Attribution will be assigned as follows:

- Definite – The AE is clearly related to the study drug.
- Probable – The AE is likely related to the study drug.
- Possible – The AE may be related to the study drug.
- Unlikely – The AE is doubtfully related to the study drug.
- Unrelated – The AE is clearly NOT related to the study drug.

Protocol must specify if attribution is required for individual components of the treatment regimen or the treatment regimen as a whole.

8.4 SAE Report Form

SAE's related to radiation therapy only will be recorded into OnCore and reported to IRB according to local IRB policies and procedures.

SAEs related to agent therapy will be recorded on the FDA Form 3500A (MedWatch) but should only be reported as instructed below. The electronic FDA SAE reporting forms should not be used.

8.5 Reporting Procedures for Serious Adverse Events

For the purposes of safety reporting, all adverse events will be reported that occur [Please insert appropriate time frame, e.g. on or following first day of RT, on day of registration, etc.] through 30 days after the final dose of study radiation therapy/drug. Adverse events, both serious and non-serious, and deaths that occur during this period will be recorded in the source documents. All SAEs should be monitored until they are resolved or are clearly determined to be due to a subject's stable or chronic condition or intercurrent illness(es). Related AEs will be followed until resolution to baseline or grade 1 or stabilization.

8.5.1 SAE Reporting Requirements

- Participating investigators (all sites) must report all serious adverse events to the Lead Site Principal Investigator (e.g. Sponsor-Investigator) within **24 hours** of discovery or notification of the event. The participating investigator must also provide follow-up information on the SAE until final resolution.
 - [name]: [contact] / [contact]
 - Study Coordinator: [name] [contact] / [contact].

- The Lead Site Principal Investigator will review the SAE and report the event to the FDA, external collaborator(s), and IRB as applicable.
- It is the Sponsor-Investigator's responsibility (e.g. lead site PI) to ensure that ALL serious adverse events that occur on the study (e.g. ALL SAEs that occur at each enrolling institution) are reported to all participating sites.

Institutional Review Board Reporting Requirements:

- Investigative sites will report adverse events to their respective IRB according to the local IRB's policies and procedures in reporting adverse events.

8.6 SAEs and OnCore

- All SAEs will be entered into OnCore.
- A copy of the SAE form(s) submitted to the sponsor-investigator is also uploaded into Oncore.

8.7 Data Safety and Toxicity Committee

It is the responsibility of each site PI to ensure that ALL SAEs occurring on this trial (internal or external) are reported to the Case Comprehensive Cancer Center's Data and Safety Toxicity Committee. This submission is simultaneous with their submission to the sponsor and/or other regulatory bodies

The sponsor-investigator is responsible for submitting an annual report to the DSTC as per CCCC Data and Safety Monitoring Plan.

8.8 Data and Safety Monitoring Plan

This protocol will adhere to the policies of the Case Comprehensive Cancer Center Data and Safety Monitoring Plan in accordance with NCI guidelines.

9.0 PHARMACEUTICAL INFORMATION

A list of the adverse events and potential risks associated with the investigational or commercial agents administered in this study can be found in Section #8.

10.0 CORRELATIVE STUDIES N/A

11.0 STUDY PARAMETERS AND CALENDAR

11.2 Calendar

Patients will be treated weekly for 3 to 6 weeks.

Follow up visits will take place at 3 and 6 month intervals.

A visit window of \pm 1 day is allowed for treatment/procedure visit

A visit window of \pm 7 days is allowed for the 3 and 6 month follow-up visits.

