2.2 Secondary Objective(s)

- a.** To collect data in order to show how the 6-tube endoesophageal brachytherapy technique will be an improvement (more conformed dose distribution) over our previously designed 3-tube endoesophageal brachytherapy technique in patients who are candidates for esophageal brachytherapy
- b.** To evaluate acute toxicity of novel endoesophageal brachytherapy applicator.

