3.4 Expected Duration of Treatment and Subject Participation

The initial treatment session will occur after the patient has been found to be eligible, the consent form has been completed, and the treatment plan has been created. The patient will undergo subsequent weekly treatments for 3 to 6 weeks after the initial treatment.

The subject will be expected to participate in the trial throughout its entirety. The participation period is 6 months of which the patient will be evaluated and seen at months 3 and 6.

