6.1.3 Target Volumes

Patients will be treated using standard radiation therapy dosing guidelines, typically in 2-6 sessions separated by weekly intervals. In addition to identifying the treatment volume (CTV, PTV), the organs at risk will be identified.

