6.8 Duration of Follow Up

Subjects will be followed for 6 months after the initial procedure or until death, whichever occurs first.

The clinical course of each event will be followed until resolution, stabilization, or until it has been determined that the study treatment or participation is not the cause.

Serious adverse events that are still ongoing at the end of the study period will necessitate follow-up to determine the final outcome. Any serious adverse event that occurs after the study period and is considered to be possibly related to the study treatment or study participation will be recorded and reported immediately.

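### No toxicity contact is scheduled between the last brachytherapy session and month 3, so acute toxicity after the full course may be under-recorded

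*Combined protocol and SAP*

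**What the plan says.** Section 2.2 gives as a secondary objective "To evaluate acute toxicity of novel endoesophageal brachytherapy applicator". Section 3.0 also lists acute toxicity among the data to be collected.

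The scheduled contacts are these:

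- **Treatment.** Section 11.2 says "Patients will be treated weekly for 3 to 6 weeks". Section 3.4 says "The patient will undergo subsequent weekly treatments for 3 to 6 weeks after the initial treatment". Sections 3.0 and 6.1.3 say "typically in 2-6 sessions separated by weekly intervals".
- **Follow-up.** Section 11.2 says "Follow up visits will take place at 3 and 6 month intervals", with a window of ± 7 days. Section 3.4 agrees: "The participation period is 6 months of which the patient will be evaluated and seen at months 3 and 6".
- **Time origin.** Section 6.8 says "Subjects will be followed for 6 months after the initial procedure or until death, whichever occurs first".

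On adverse events, 8.5 closes the reporting period 30 days after the final dose. Section 8.3.3 covers events that the team observes or the subject reports. For each it asks for the CTCAE term, grade, attribution, and onset and resolution dates. Appendix II has columns for tumor response, ulceration, fistula, stricture and dilation. It has none for acute toxicity or a CTCAE grade.

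**The concern.** After every session but the last, the subject returns about a week later for the next one, so the team at least has an occasion to ask about symptoms. The last session comes when the cumulative dose and the number of applicator insertions are at their highest. After it, the text provides about half an hour of vital-sign monitoring before discharge and then no planned contact until month 3.

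Serious events will probably come to notice anyway. Non-serious ones, such as pain on swallowing or minor bleeding, may not. If one arises and settles before month 3, its grade and dates depend on the subject having called in or remembering it weeks later. Acute toxicity is one of two secondary objectives, and the part of the course with the greatest exposure has the weakest ascertainment.

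**Working it through.** The plan states no gap length, so there is no figure of its own to reproduce. The check is date arithmetic.

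**Inputs**

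- Sessions are weekly, so with the initial procedure as day 0 the last of *n* sessions falls on day 7 × (*n* − 1).
- Session counts: 3 to 6 (11.2, and the protocol summary's cycle count); 2 to 6 (3.0 and 6.1.3); 4 to 7 (3.4, read as an initial session plus 3 to 6 weekly ones).
- Month 3 is taken as day 91 (13 weeks) from the initial procedure. Day 91 is an assumption; the origin follows 6.8. With the ± 7-day window of 11.2, the visit falls on days 84 to 98.
- The 8.5 period ends on the day of the last session + 30.

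**Formulas**

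Gap = day of month-3 visit − day of last session. Margin = 84 − (day of last session + 30), the time from the close of the 8.5 period to the earliest permitted month-3 visit.

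| Sessions | Last session (day) | Gap at day 91 | Gap at days 84 to 98 | 8.5 period ends (day) | Margin (days) |
|---|---|---|---|---|---|
| 2 | 7 | 84 | 77 to 91 | 37 | 47 |
| 3 | 14 | 77 | 70 to 84 | 44 | 40 |
| 4 | 21 | 70 | 63 to 77 | 51 | 33 |
| 6 | 35 | 56 | 49 to 63 | 65 | 19 |
| 7 | 42 | 49 | 42 to 56 | 72 | 12 |

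**Results**

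- For 3 to 6 sessions the gap is 49 to 84 days, that is 49/7 = 7 to 84/7 = 12 weeks.
- Across all the wordings it is 42 to 91 days, that is 6 to 13 weeks. The ± 1-day treatment window moves each end by one day, to 41 and 92.
- In every row the 8.5 period closes before the earliest month-3 visit, by 12 days or more on nominal session days. No follow-up visit falls inside the reporting period.
- If month 3 were instead counted from the last session, the gap would be 84 to 98 days (12 to 14 weeks), so the choice of origin does not create the problem.

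**Does anything else fill the gap?** The weekly review in 8.1 applies during external beam treatment and lists bowel, urinary and skin effects. Section 8.5 sets a recording duty but attaches no visit, call or questionnaire. Section 12 and Appendix II do not prompt for acute toxicity at any visit.

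**Scale.** With about 5 subjects (3.2), one unrecorded case moves an observed proportion by 1/5 = 20 percentage points. No threshold or stopping rule in the plan uses that proportion, so this only indicates how coarse the estimate is.

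**The case against.** The strongest reply is that the duty to record already exists. Section 8.3.3 requires all observed or reported events to be recorded and graded, 8.5 covers serious and non-serious events to 30 days, and 6.8 follows each event to resolution or stabilization. That stands. A reader might infer that an event resolving before month 3 would never be graded by anyone, and the documents do not support this: an event the subject reports must be graded. What is missing is a scheduled occasion to ask.

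A reader might also infer that the applicator will look better tolerated than it is. That goes too far. The documents give no time course for acute esophageal effects and do not say how toxicity was ascertained in the historical controls. Under-recording is a possibility, and its effect on any comparison is unknown.

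Absence is also not fully proven. Section 13.1 says that a calendar of events and the required forms are held in OnCore, and the study schema is not visible. An extra contact could be listed there. If so, 11.2 should state it.

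The weekly sessions are not a firm baseline either. The procedure text describes vital signs, endoscopy, imaging and treatment, but no toxicity grading. This objection stands and widens the remedy, since a late call alone would leave grading during treatment unspecified.

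Finally, this is a pilot of about five subjects with a dosimetric primary objective, and ulceration, fistula, stricture and dilation have their own fields. That limits the weight of the point but does not remove it, because the remedy is so small.

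**Conclusion.** The point holds as a gap in scheduled ascertainment. On the protocol text, non-serious acute toxicity after the full course is captured only if the subject volunteers it or recalls it at month 3. That is about 7 to 12 weeks after the last session for 3 to 6 weekly sessions, or 6 to 13 weeks across the conflicting session counts. Acute toxicity may therefore be under-recorded.

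This rests on three things: month 3 taken as day 91 ± 7, counted from the initial procedure; weekly sessions on their nominal days; and no further contact in the OnCore calendar, which could not be seen. The conclusion does not depend on which session count is meant, because the gap exceeds the 30-day reporting period under all of them. It is a worthwhile, low-cost improvement and does not touch the primary objective.

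**What to change.** 1. Add to 11.2 one scheduled toxicity contact about 30 days after the final session, where the 8.5 period already ends. The existing coordinator can make it by telephone. Record the CTCAE v4.0 term, the worst grade since the last session, and the onset and resolution dates. An investigator assigns grade and attribution, as 8.3.3 provides for attribution.
2. Record the same CTCAE items at each weekly session, before that day's treatment.
3. Add these fields to Appendix II, and state in section 14 that acute toxicity will be reported from the weekly contacts and the 30-day contact.
4. Reconcile the session counts in 3.0, 3.4, 6.1.3 and 11.2, and state in 11.2 the origin from which months 3 and 6 are counted. If OnCore already lists a post-treatment contact, carry it into 11.2.

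The cost is about five short calls, a calendar line, a few form fields, and slight extra coordinator and patient time. Treatment and sample size do not change. The call still relies on recall over up to 30 days, so it shortens the recall period without removing it.

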12.0 MEASUREMENT OF EFFECT

- Tumor Response: CR, PR, SD, PD
- Esophageal Ulceration
- Esophageal Fistula
- Esophageal Stricture
- Need for Dilation

13.0 DATA REPORTING / REGULATORY CONSIDERATIONS

Adverse event lists, guidelines, and instructions for AE reporting can be found in Section 8.0 (Adverse Events: List and Reporting Requirements).

13.1 Data Reporting

The OnCore™ Database will be utilized, as required by the Case Comprehensive Cancer Center, to provide data collection for both accrual entry and trial data management. OnCore™ is a Clinical Trials Management System housed on secure servers maintained at Case Western Reserve University. OnCore™. Access to data through OnCore™ is restricted by user accounts and assigned roles. Once logged into the OnCore™ system with a user ID and password, OnCore™ defines roles for each user which limits access to appropriate data. User information and password can be obtained by contacting the OnCore™ Administrator at [contact].

OnCore™ is designed with the capability for study setup, activation, tracking, reporting, data monitoring and review, and eligibility verification. This study will utilize electronic Case Report Form completion in the OnCore™ database. A calendar of events and required forms are available in OnCore™.

13.2 Regulatory Considerations

The study will be conducted in compliance with ICH guidelines and with all applicable federal (including 21 CFR parts 56 & 50), state or local laws.

13.2.1 Written Informed consent

Provision of written informed consent must be obtained prior to any study-related procedures. The Principal Investigator will ensure that the subject is given full and adequate oral and written information about the nature, purpose, possible risks and benefits of the study as well as the subject's financial responsibility. Subjects must also be notified that they are free to discontinue from the study at any time. The subject should be given the opportunity to ask questions and be allowed time to consider the information provided.

The original, signed written Informed Consent Form must be kept with the Research Chart in conformance with the institution's standard operating procedures. A copy of the signed written Informed Consent Form must be given to the subject. Additionally, documentation of the consenting process should be located in the research chart.

13.2.2 Subject Data Protection

In accordance with the Health Information Portability and Accountability Act (HIPAA), a subject must sign an authorization to release medical information to the sponsor and/or allow the sponsor, a regulatory authority, or Institutional Review Board access to subject's medical

information that includes all hospital records relevant to the study, including subjects' medical history.

13.2.3 Retention of records

The Principal Investigator of The Case Comprehensive Cancer Center supervises the retention of all documentation of adverse events, records of study drug receipt and dispensation, and all IRB correspondence for as long as needed to comply with local, national and international regulations. No records will be destroyed until the Principal Investigator confirms destruction is permitted.

13.2.4 Audits and inspections

Authorized representatives of the sponsor, a regulatory authority, an Independent Ethics Committee (IEC) or an Institutional Review Board (IRB) may visit the site to perform audits or inspections, including source data verification. The purpose of an audit or inspection is to systematically and independently examine all study-related activities and documents to determine whether these activities were conducted, and data were recorded, analysed, and accurately reported according to the protocol, Good Clinical Practice (GCP), guidelines of the International Conference on Harmonization (ICH), and any applicable regulatory requirements. For multi-center studies, participating sites must inform the sponsor-investigator of pending audits.

14.0 STATISTICAL CONSIDERATIONS

This section outlines the statistical analysis strategy and procedures for the study. If, after the study has begun, changes made to primary and/or key secondary hypotheses, or the statistical methods related to those hypotheses, then the protocol will be amended (consistent with ICH Guideline E-9).

A variety of statistical methods will be employed to analyze the trials's data. Data will be periodically analyzed using descriptive statistics and correlative measures for significance when comparing demographic and dosimetric data. Typical dosimetry constraints, such as the dose delivered to 90% of the tumor volume (D90) and the volume of the tumor receiving the prescription dose (V100) will be reviewed to ensure that an acceptable treatment plan is designed. The use of our new applicator will improve the dose homogeneity as well as lower the dose to the nearby normal organs.

As this application is specifically for a new device to deliver the same doses of radiation therapy previous administered using single or multi-tube approaches, we will analyze data on patient outcome and dosimetry data in comparison with our historical controls. Specifically, we will use endoscopic follow-up images and correlate the visual changes with the radiation therapy doses delivered to the tumor, esophageal wall, and nearby organs at risk. One of the limitations of esophageal brachytherapy is the lack of the treating physician's ability to modulate the dose when using a single tube device.

The currently utilized and innovative approach used in our department is a 3-tube technique. Use of the 3-tube technique improves the dose homogeneity and reduces the doses to heart, lungs, bronchus, trachea, and vertebral bodies. In addition to nonoperable patients with esophageal cancer undergoing definitive therapy, patients with recurrent or metastatic disease may symptomatically benefit from HDR brachytherapy. In fact, a randomized controlled trial

